**Exploratory Objectives**

Study Design:	
This is a randomized, double-blind study, with an open-label extension, to be conducted at approximately 18 centers in the United States (US). Male and female subjects, 18-65 years old (inclusive), previously diagnosed with episodic migraine (at least 12 months medical history prior to screening) who do not have medication overuse headaches (MOH), who experience 2 to 6 migraine attacks (with or without visual aura) per month, with 14 or fewer migraine headache days per month, and who can demonstrate 48 hours of headache free time between migraine attacks, will be initially randomized in a 1:1 ratio in a double-blind fashion to receive by subcutaneous (SC) injection either DFN-11 or placebo, to be used in 1 migraine attack within 1 hour of experiencing moderate to severe pain level. This double-blind period is up to 4 weeks (+ 3 days) or within 5 days (+ 3 days) postdose, whichever is earlier, depending on when, and if, the subject will get migraine attack during the double-blind period. Subjects may subsequently continue into an open-label period where they will receive active DFN-11 for 8 weeks to treat their migraine within 1 hour of migraine pain onset at any pain level.
 
During the 2 treatment periods, data regarding the study medication effect and the associated impact on function and subjects' satisfaction will also be collected. All subjects will receive the study medication via self-administered SC injections (DFN-11 or placebo) using an autoinjector during the study. After study completion or discontinuation, subjects should be referred to their usual healthcare professional to resume pre-study standard of care, as per the Investigator's discretion. Subjects will return the autoinjector to the study site at the end of the study.
 
During both treatment periods of the study, subjects will have an option to take another dose of study medication, if they experience relief but feel the first dose is insufficient, or rescue medication 2 hours after the first dose of study medication if required and after the efficacy data has been recorded. No more than 2 doses of study medication will be taken in a 24 hour period. Rescue medication will be decided between the Investigator and the subject.

Selection of Subjects:	
Main Inclusion Criteria:
 
Subjects may be included in the study if they meet the following criteria:

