	

1. Able and willing to provide written informed consent

2. Male or female, 18 to 65 years of age, inclusive, at screening

 
Notes:
 

a. If female, a subject must have a negative serum pregnancy test at screening, does not plan to become pregnant during the study, and is not lactating

b. If female, a subject also must have a negative urine pregnancy test at all subsequent study visits after the Screening Visit, and agree to practice a reliable form of contraception or abstinence during the study (except if surgically, or otherwise, sterile or >1 year post-menopausal). Acceptable forms of contraception include implants, injectables, combined oral contraceptives, an intrauterine device, a vasectomized partner, an exclusively female partner, and double-barrier methods.

c. If male (with female partner), a subject must agree to practice a reliable form of contraception or abstinence during the study.

 

3. A history of episodic migraine (using International Classification of Headache Disorders criteria, 2nd edition [ICHD II]) who experience 2 to 6 migraine attacks a month for at least the past 12 months with no more than 14 migraine headache days per month, and with 48 hours of headache free time between migraine headaches

4. Have migraine with or without aura; if with aura, the aura cannot last longer than 60 minutes

5. Subjects who, in the opinion of the Investigator, are willing and able to:

• Evaluate and record pain, migraine symptoms, and study medication effectiveness information in real time using a subject eDiary for the duration of the study

• Record each instance of the use of study medication and rescue medication in real time using a subject eDiary for the duration of the study

• Comply with all other study procedures and scheduling requirements

--	--

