Study Endpoints:	
Primary Endpoints:
 
Double-Blind Period (Period 1)
 
The proportion of subjects who are pain-free (defined as a reduction from predose moderate [Grade 2] or severe [Grade 3] pain to none [Grade 0]) 2 hours after the first dose of study medication compared between DFN-11 and placebo in the double-blind period.
 
Key Secondary Endpoints:
 
Double-Blind Period (Period 1)
 

• [REDACTED]

• The proportion of subjects who are pain-free (defined as a reduction from predose moderate [Grade 2] or severe [Grade 3] pain to none [Grade 0]) 1 hour after the first dose of study medication compared between DFN-11 and placebo in double-blind period.

• The proportion of subjects who are free from their MBS among nausea, photophobia, and phonophobia 2 hours after the first dose of study medication compared between DFN-11 and placebo in double-blind period.

 
Other Secondary Endpoints:
 
Double-Blind and Open-Label Extension (Period 1 and Period 2)
 
Efficacy Endpoints
 
The secondary efficacy endpoints are as follows:
 

• [REDACTED]

	

• The proportion of subjects who have pain relief [REDACTED]

• The proportion of subjects who are pain-free [REDACTED]

• The proportion of subjects with their MBS absent [REDACTED]

• Change in functional disability score [REDACTED]

• The proportion of subjects who use a second dose of the study medication or rescue medication after 2 hours (2-24 hours) postdose study medication compared between DFN-11 and placebo in double-blind period, and DFN-11

--	---

in the open-label period

- Treatment satisfaction at 2 hours postdose as determined on a 7 point scale after study medication compared between DFN-11 and placebo in double-blind period, and DFN-11 in the open-label period.
- Treatment satisfaction as measured by PPMQ-R at 24 hours postdose study medication compared between DFN-11 and placebo in double-blind period, and DFN-11 in the open-label period.

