## Exploratory Endpoints:

A high-contrast, black and white image showing a series of horizontal bars of varying lengths. The bars are mostly black on a white background, with some white bars appearing on the right side. A small orange dot is located at the bottom left.

	

• [REDACTED]

[REDACTED]

[REDACTED]

[REDACTED]

[REDACTED]

Statistical Methods and Planned Analyses:	The statistical analysis method for the primary endpoint is described below. Detailed analyses of secondary and exploratory endpoints will be provided in the Statistical Analysis Plan (SAP), which will be finalized before database lock and unblinding of the data.

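### Must the second-dose or rescue endpoint name an attack for the open-label period, where one subject may treat several?

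*Combined protocol and SAP*

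**What the plan says.** In the Synopsis, Study Endpoints, the other secondary endpoints stand under a heading that covers Period 1 and Period 2. One of them is "The proportion of subjects who use a second dose of the study medication or rescue medication after 2 hours (2-24 hours) postdose study medication". It continues "compared between DFN-11 and placebo in double-blind period, and DFN-11" and, after a table break, ends by naming the open-label period. The matching objective uses the same terms and also names no attack.

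Study Design gives the exposure in each period. Double-blind drug is "to be used in 1 migraine attack within 1 hour of experiencing moderate to severe pain level". Subjects who continue enter a period "where they will receive active DFN-11 for 8 weeks to treat their migraine within 1 hour of migraine pain onset", at any pain level. A second dose or rescue medication is an option in both periods. Eligible subjects have 2 to 6 attacks a month.

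The primary endpoint is anchored more tightly, at "2 hours after the first dose of study medication compared between DFN-11 and placebo in the double-blind period". Statistical Methods and Planned Analyses leaves the detail of secondary analyses to a SAP "which will be finalized before database lock and unblinding of the data". Under Selection of Subjects, participants must be able to "Record each instance of the use of study medication and rescue medication in real time" in the eDiary.

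**The concern.** The endpoint counts subjects, but the number of chances to be counted differs by period. A double-blind subject has one window of 2 to 24 hours. An open-label subject has one window for each treated attack. Read literally, a subject who takes rescue medication after any one of those attacks is a subject who uses it. The open-label proportion would then reflect attack frequency as well as the drug, and a reader might set it beside the double-blind figure as if the two measured the same thing.

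Two other features seem to strengthen the point. The primary and 1-hour endpoints refer to the first dose, and this one does not. The SAP deadline is tied to database lock and unblinding, and open-label treatment is known to everyone, so unblinding gives no protection against choosing the unit after open-label results have been seen.

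The open-label satisfaction endpoints, such as the one on the "7 point scale after study medication compared between DFN-11 and placebo in double-blind period, and DFN-11 in the open-label period", name no attack either. They are not proportions of subjects who ever had an event, so they would not rise mechanically in the same way.

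**Working it through.** The plan gives no rate, power or expected value for this endpoint, so there is no stated figure to reproduce. The check asks how much the any-attack reading could matter.

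**Inputs from the documents.** One treated attack in the double-blind period; 8 weeks (56 days) open-label; 2 to 6 attacks a month at entry.

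**Inputs assumed.** Probability p that a treated attack leads to a second dose or rescue; within-subject correlation rho; number n of attacks treated. The documents give none of these.

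**Attacks in 56 days, with a 30.44-day month.** 2 × 56/30.44 = 3.7 and 6 × 56/30.44 = 11.0. The number treated is not stated, so these are attacks available to treat.

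**Any-attack proportion, independent attacks.** 1 − (1 − p)^n. With p = 0.3: n = 1 gives 30%; n = 2 gives 1 − 0.7² = 51%; n = 4 gives 1 − 0.7⁴ = 76%.

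**Any-attack proportion, correlated attacks (beta-binomial).** Let k = 1/rho − 1, a = pk and b = (1 − p)k. The proportion is 1 − ∏ (b + i)/(a + b + i), for i = 0 to n − 1.

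With p = 0.3 and rho = 0.3: k = 2.333, a = 0.7, b = 1.633.
- n = 2: 1 − (1.633/2.333)(2.633/3.333) = 1 − 0.700 × 0.790 = 44.7%.
- n = 4: 1 − 0.553 × (3.633/4.333)(4.633/5.333) = 1 − 0.553 × 0.838 × 0.869 = 59.7%.

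**Dependence on the correlation, p = 0.3.**

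| rho | n = 1 | n = 4 | n = 8 | n = 12 |
|---|---|---|---|---|
| 0 | 30% | 76% | 94% | 99% |
| 0.2 | 30% | 65% | 80% | 86% |
| 0.5 | 30% | 51% | 59% | 64% |
| 0.8 | 30% | 38% | 41% | 43% |

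The proportion rises in every row. At 4 attacks the rise runs from 8 to 46 percentage points, depending only on an assumed correlation.

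**Other units.** With a per-attack or first-attack unit, the expected value is p whatever n is, provided use does not depend on attack number or frequency. Each unit has a cost. If every attack were treated, the first would be 1/3.7 = 27% of a subject's attacks at the low end of eligibility and 1/11.0 = 9% at the high end, so a first-attack rule discards most of the open-label data. A pooled per-attack proportion keeps the data but gives a subject with 11.0 attacks about 11.0/3.7 = 3.0 times the weight of one with 3.7.

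**The case for a change.** The strongest case for a change is that the gap is real and cheap to close. The sentence is legible in full, it covers two periods with different exposure, and it names no attack. The direction of the any-attack effect does not depend on the assumptions. One sentence would settle the unit, and no new data are needed. All of that stands as a description of the text.

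The step from there to a defect in the plan does not stand:

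- The endpoint does not say any attack, or at least once. Its window is set from a dose, which fits a per-attack reading at least as well. The rise therefore follows from one reading only.
- The contrast with the primary and 1-hour endpoints shows little. Those apply only to the double-blind period, where there is one attack. There, the first dose is distinguished from the optional second dose in the same attack, not from later attacks.
- The text available is a synopsis, and it says that detail on secondary endpoints belongs in the SAP. Several neighbouring endpoints are partly or wholly redacted, so a convention on attacks may be stated where it cannot be seen.
- On timing, the open-label period has one treatment, so there is no between-arm contrast to exploit. Nothing visible says that open-label efficacy would be tabulated before the SAP is final.
- Naming the unit would not make the two periods comparable. They also differ in blinding, in optional entry, and in pain level at treatment: moderate to severe in one, any level in the other.

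**Conclusion.** No change to the plan is needed. This is missing detail in a synopsis bullet, of a kind that analysts must settle before they can produce the table. The diary is to capture each use of study and rescue medication, so the first-attack, per-attack and any-attack summaries can all be derived, along with the number of attacks treated per subject. The choice between them is a trade-off between using all the data and weighting subjects equally, and the documents do not make one answer compulsory.

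Little is at stake. The only figure affected is a single-arm secondary proportion. The endpoint compares DFN-11 with placebo in the double-blind period only, and no visible text plans a comparison between periods. The double-blind comparison rests on one attack per subject, and the primary and key secondary analyses do not use this endpoint.

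The illustrative values, such as 38% to 76% at 4 attacks against 30% for one, rest wholly on an assumed rate and assumed correlations of 0 to 0.8. They show the direction under one reading and are not an estimate for this trial. The conclusion assumes that the SAP, or the analysts applying it, will state the unit when the open-label figure is reported. It would need another look if that figure were published as an any-attack proportion and set directly against the double-blind one.

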## *Safety Endpoints*

The safety endpoints of this study are as follows:

- Proportion of subjects with treatment emergent adverse events (TEAEs) and SAEs after study medication compared between DFN-11 and placebo in double-blind period, and DFN-11 in the open-label period.
- Changes in the clinical laboratory tests, vital signs, and ECG after study medication for DFN-11 and placebo in the double-blind period, and DFN-11 in the open-label period.

## Exploratory Endpoints:

A high-contrast, black and white image showing a series of horizontal bars of varying lengths. The bars are mostly black on a white background, with some white bars appearing on the right side. A small orange dot is located at the bottom left.

	

• [REDACTED]

[REDACTED]

[REDACTED]

[REDACTED]

[REDACTED]

Statistical Methods and Planned Analyses:	The statistical analysis method for the primary endpoint is described below. Detailed analyses of secondary and exploratory endpoints will be provided in the Statistical Analysis Plan (SAP), which will be finalized before database lock and unblinding of the data.

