	
3 months prior to screening and is expected to remain stable throughout the study
 
Note: For the above-mentioned conditions, the site must have appropriate documentation to justify the mentioned drug use (e.g., documented medical history and a valid prescription-based dispensation)
 

33. A history of or current neurological or psychiatric impairment, including but not limited to psychosis, current major depression, bipolar disorder or cognitive dysfunction that, in the opinion of the Investigator, would compromise data collection

34. Subjects who have received treatment with an investigational drug or device within 30 days of the screening visit or participated in a central nervous system clinical trial in the 3 months prior to screening

35. Subjects with any other medical condition that, in the judgment of the Investigator and/or Medical Monitor, would confound the objectives of the study (e.g., positive screening test for human immunodeficiency virus [HIV], hepatitis B surface antigen positive or hepatitis C positive, a known history of systemic lupus erythematosus)

36. History of cancer within the past 5 years (except adequately treated basal cell or squamous cell skin carcinoma or in situ cervical cancer)

37. History of any skin condition that may adversely affect the injection or use of subcutaneously administered medication such as scleroderma

38. Subjects who should not be enrolled per the precautions, warnings, and contraindications section of the Imitrex® product label or package insert

39. Subjects who plan to donate blood, sperm, or oocytes during the study and for 30 days after the last dose of study medication

40. Subjects who are employees or immediate relatives of the employees of the Sponsor, any of its affiliates or partners, or of the study center

Planned Sample Size:	A total of approximately 266 subjects will be randomized in a 1:1 ratio into 2 treatment arms. The study may be stopped sooner based on an independent Data Monitoring Committee (DMC) recommendation after reviewing study efficacy data

	(see Statistical Methods and Planned Analysis section for details) at an interim analysis (IA).
Investigational Therapy:	DFN-11 Injection (sumatriptan 3 mg)
Reference Therapy:	Placebo injection

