### **Primary Efficacy Analysis**

The primary efficacy analysis will be performed using Fisher's exact test.

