#### **Interim analysis**

One or more interim analyses (IA) for potential early stopping for an efficacy conclusion are planned

A conservative alpha spending function will be used to preserve most of the type 1 error for the final analysis in case the trial does not stop for an efficacy conclusion at IA(s).

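### Could the analysis plan be completed after the data monitoring committee has already looked at efficacy?

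*Combined protocol and SAP*

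**What the plan says.** All of the text is in Section 1 (Synopsis) of the combined protocol and SAP.

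- **Statistical Methods and Planned Analyses** divides the work in two. For the primary endpoint, "The statistical analysis method for the primary endpoint is described below". For the rest, "Detailed analyses of secondary and exploratory endpoints will be provided in the Statistical Analysis Plan (SAP"), a document "which will be finalized before database lock and unblinding of the data".
- **Primary Efficacy Analysis** fixes the test: "The primary efficacy analysis will be performed using Fisher's exact test".
- **Planned Sample Size** provides for early stopping: "The study may be stopped sooner based on an independent Data Monitoring Committee (DMC) recommendation after reviewing study efficacy data".
- **Interim analysis** states "One or more interim analyses (IA) for potential early stopping for an efficacy conclusion are planned", and then "A conservative alpha spending function will be used to preserve most of the type 1 error for the final analysis" if the trial continues past the interim.

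No visible sentence gives the family of the spending function, the number or timing of looks, or a testing order for the key secondary endpoints. Two of those endpoints can be read (pain freedom at 1 hour and freedom from the most bothersome symptom at 2 hours), and a further bullet is redacted.

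**The concern.** An interim efficacy comparison comes before database lock and can end the trial. If lock is the only effective deadline for the SAP, its contents could be settled once unblinded comparative data exist. Alpha spending controls type I error only when the function is fixed before the first look and the timing of looks does not depend on results. Conservative is a loose word: at half the information, two functions that both deserve it differ about twofold in the alpha they release. An interim p-value of 0.004 would stop the trial under one and not under the other.

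The key secondaries are the more exposed part, because their analysis is expressly deferred to the SAP. If the trial stopped early, they would be called on as confirmatory results at once, and a testing order written after the stop would be open to challenge.

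**Working it through.** **1. The deadline.** The sentence names two events, database lock and unblinding of the data. A committee comparing efficacy between arms needs treatment codes, so its first review can be read as an unblinding, which puts the SAP before the first look. The other reading, final unblinding of the study, is also possible. The text does not decide between them, so it cannot be cited as permitting a late SAP.

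**2. What is deferred.** The same sentence gives the SAP the secondary and exploratory analyses. The boundary is dealt with under Interim analysis and is not assigned to the SAP. The date of the SAP therefore does not show when the boundary is fixed. A boundary is needed to judge the first interim at all.

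**3. What can be seen.** Only the Synopsis is available. Exclusion criterion 19 refers to Section 7.3, so a protocol body exists. The sentence on planned interims ends without a full stop, next to heavily redacted material. Missing detail on looks and function cannot be counted as absent from the plan.

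**4. Size of the boundary risk.** The plan's only design figure is about 266 subjects. It cannot be reproduced, because the visible text gives no alpha, power or response rates, and this point does not depend on it. Assumptions: two-sided alpha 0.05, one look at information fraction t, with t from 1/3 to 3/4.

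Alpha released at t = 0.5:

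- O'Brien-Fleming type: 4[1 − Φ(2.2414/√0.5)] = 4[1 − Φ(3.170)] = 0.0031
- Hwang-Shih-DeCani, γ = −4: 0.05(1 − e²)/(1 − e⁴) = 0.05 × 6.389/53.598 = 0.0060
- Haybittle-Peto: 0.001 by definition
- Pocock type: 0.05 ln[1 + (e − 1) × 0.5] = 0.0310

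The final critical value c₂ solves P(Z₁ > c₁ or Z₂ > c₂) = 0.025 with correlation √t. At t = 0.5 the final two-sided p-value thresholds are 0.0490, 0.0476, 0.0498 and 0.0277 in the same order. Each rule, fixed in advance, holds overall alpha at 0.05. The twofold ratio 0.0060/0.0031 is therefore a difference in how two valid rules share out alpha, and does not measure error inflation.

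Inflation arises only if someone takes the more lenient boundary of a pair at each look after seeing the result. Overall two-sided error is then 2P(Z₁ > min c₁ or Z₂ > min c₂):

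| t | O'Brien-Fleming / Haybittle-Peto | O'Brien-Fleming / Hwang-Shih-DeCani | Hwang-Shih-DeCani / Haybittle-Peto |
|---|---|---|---|
| 1/3 | 0.0504 | 0.0513 | 0.0509 |
| 1/2 | 0.0508 | 0.0514 | 0.0521 |
| 2/3 | 0.0534 | 0.0502 | 0.0536 |
| 3/4 | 0.0551 | 0.0507 | 0.0545 |

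The largest value in each row is also the worst case over all three rules: 0.051, 0.052, 0.054 and 0.055.

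Pairing O'Brien-Fleming with Pocock type would give 0.063 to 0.068. Pocock spending uses 0.031/0.05 = 62% of alpha at half the information, which contradicts the commitment to keep most of it for the final analysis. At t = 1/3 it uses 0.0226/0.05 = 45%, which meets that clause literally but is not what conservative means.

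**5. Key secondaries.** Two independent tests at 0.05, both nulls true, give 1 − 0.95² = 0.0975. That is the cost of having no multiplicity rule. It is the same whether the SAP is signed early or late, so it does not measure the effect of the date.

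**The case for a change.** The strongest reply is that unblinding sits beside database lock, and the pair most naturally describes the end of the study. On that reading no visible sentence requires anything to be final before the first look. An independent committee lowers the risk but does not remove it: a decision to stop for efficacy tells the SAP's authors that the primary comparison succeeded, and the key secondaries are likely to be correlated with it. If there is a single lock after the 8-week open-label period, the gap could be long. One sentence would close it at almost no cost.

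Part of this stands. The wording is ambiguous, and an explicit date would be tidier. But knowing that the trial stopped is not the same as seeing the secondary results by arm. Even on the end-of-study reading, the SAP must still be final before the data are unblinded, so a stop does not release the secondary comparisons to its authors first. The argument applies to the key secondaries and does not extend to the primary test or to the boundary.

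**Conclusion.** No change to the plan is needed. This is a gap that analysts fill sensibly. Followed as written, the primary conclusion is sound: the test is named, a conservative spending function is promised and has to exist before an interim can be judged, and an independent committee in a double-blind trial does the review. The key-secondary rules would be set by people who, on the visible text, have not been shown results by arm.

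If a conservative boundary were nevertheless chosen with the result in hand, overall error would be 0.051 to 0.055 against 0.05. That range assumes two-sided alpha of 0.05, a single look between one third and three quarters of the information, and a choice among the three conservative rules computed. More than one look was not computed. The conclusion would weaken if the full protocol showed that those who write the SAP have access to unblinded interim results.
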